6.3.2.2. Classifying Participants into Process-Specific Groups

We aim to identify M-STBI patients whose injuries produce primary deficits in encoding/acquisition, consolidation/retention, or retrieval. While we expect that many patients may have some problems in more than one domain, many studies have concluded that memory problems after M-STBI are *primarily* rooted in one of these domains at the individual level^{5-7,56,57}. Three studies^{4,7,58} report distinct deficit patterns attributable to encoding, consolidation, and retrieval deficits using the CVLT⁵⁹. Crosson et al⁷ found that encoding deficits were marked by a high false positive (FP) rate and reduced hits on recognition, while consolidation deficits were marked by lower hit rates and lower FP (also see⁵⁸). Curtiss et al⁵⁶, using hierarchical clustering of CVLT and WMS-R variables, found three memory-impaired groups corresponding to acquisition/encoding, retention, and retrieval deficits. Millis and Ricker⁴ used Delis⁵⁹ six-factor solution of CVLT performance variance to identify patterns of verbal learning deficit after moderate-severe TBI. They found 4 identifiable clusters: a Disorganized type (n = 22; encoding deficit) who exhibited a haphazard learning style, elevated FP rate, reduced discriminability on recognition testing and increased susceptibility to proactive interference, an Active type (n = 15; retrieval deficit) who showed good semantic encoding, good acquisition rate, and disproportionate improvement on recognition (discriminability), a Passive type (n = 11; consolidation deficit) whose recall showed prominent serial position effects and rapid forgetting, and a Deficient type (n = 13; encoding deficit) who showed slow rate of learning, recency effects in free recall, and an excessively high FP rate on recognition. These results were subsequently replicated and extended³. We will use this classification scheme, summarized in Table 2. Deficient and Disorganized groups will be collapsed, as both suffer from encoding deficits. Characteristics of each class (encoding, consolidation, and retrieval) will be combined in multivariate fashion, creating a composite score. Participants will be assigned to the group corresponding to the most impaired composite score. We will also investigate other algorithms for classifying patients, with the goal of deriving the most accurate and stable method.

Table 2. Scheme for Classifying TBI patients into deficit categories.

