## 2.6. Statistical Analysis Plan

The procedure for classifying participants into Encoding, Consolidation, and Retrieval groups is outlined in Section 2.3.2. It is recognized that, although patients will be classified according to their primary memory deficit, some may have relevant impairment in more than one domain. For this reason, each participant will be given a composite score for encoding, consolidation, and retrieval, and all three of these composite scores will be used in exploratory analyses of predictors of treatment response. Phase 2 neuropsychological scores (z-score transformed data using appropriate age- and education corrections) and neuroimaging data (NEW, FA, diffusivity measures, morphological volumes, TI from RS-fMRI for specific ROI pairs) will be analyzed using 1-way (Group: Encoding, Consolidation, Retrieval) ANOVAs followed by pairwise follow-ups with the Tukey HSD test. Dependent variables used to evaluate memory performance in Phase 3 are detailed in Section 2.2 above, and include session-wise percent correct data on VPA and FNP memory probes as well as post-treatment and 1-month follow-up probes. Data from Phase 3 will be analyzed by comparing effect sizes of matched and unmatched treatments at the individual subject level using methods described by Parker et al. These measures include (a) percentage of non-overlapping data points, (b) quantitative measures of improvement rate and difference level, and (c) Tau-U, a nonparametric measure of effect size that tests for differences in two treatments after trend adjustment. Additional measures will also be explored, including interrupted time-series/regression approaches and the last-day-of-treatment comparison approach. We will also evaluate the separate influence that severity of memory deficit has on treatment response (independent of patient grouping) by performing hierarchical linear regression in which severity is coded as average z-score on memory indices derived from phase 2, and patient grouping is dummy-coded.

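### SAP 2.6 applies group ANOVAs to CVLT-II scores although the groups are built from CVLT composites, so p-values for scores that feed the classifier say nothing about whether subtypes exist

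*SAP*

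**What the plan says.** **Forming the groups.** Protocol 6.3.2.2 adopts a published CVLT scheme: "We will use this classification scheme, summarized in Table 2". Both blocks of variables in Table 2 are CVLT variables (factor scores and performance features). The rule is: "Characteristics of each class (encoding, consolidation, and retrieval) will be combined in multivariate fashion, creating a composite score", and then "Participants will be assigned to the group corresponding to the most impaired composite score". The section also leaves room for change: "We will also investigate other algorithms for classifying patients, with the goal of deriving the most accurate and stable method".

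**Testing the groups.** SAP 2.6 takes as dependent variables "Phase 2 neuropsychological scores (z-score transformed data using appropriate age- and education corrections") together with the imaging measures. These "will be analyzed using 1-way (Group: Encoding, Consolidation, Retrieval) ANOVAs followed by pairwise follow-ups with the Tukey HSD test".

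**The overlap.** Protocol Table 1 lists the CVLT-II under Memory among the Phase 2 measures. SAP 2.6 neither excludes classifier inputs nor marks their tests as descriptive. For the classification procedure it points to a Section 2.3.2; the matching text in the published documents is Protocol 6.3.2.2.

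**The concern.** A one-way ANOVA asks whether group means differ, on the footing that membership was settled without looking at the score under test. Here membership is decided by the score, or by a composite containing it. Patients whose encoding composite is worst are placed in the Encoding group, so that group does worse on encoding features whether or not a distinct encoding subtype exists.

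A team following SAP 2.6 could therefore report significant CVLT-II differences between groups, with Tukey pairs, drawn from a patient population with no subtypes at all. A reader could take them as support for the three-way classification. The study's premise is that such subtypes can be identified, so this is an easy misreading to invite.

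**Working it through.** The documents give no alpha, power or sample-size figure for these ANOVAs, so there is nothing to reproduce. The check asks how far the assignment rule alone separates the groups.

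**Inputs from the documents**
- Three composites; assignment to the most impaired (Protocol 6.3.2.2).
- Variables per class, counted from Table 2: encoding 5 + 3 = 8; consolidation 5 + 5 = 10; retrieval 5 + 5 = 10.
- 4 patients per group (Protocol 6.4.2). This is the Phase 3 figure; no Phase 2 number is given.

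**Assumptions**
- No true subtypes, normal scores, test at 5%.
- Common correlation r between composites.
- A score correlates L with its own composite (its loading) and with the others only through r.
- 8 per group is used only to show the trend.

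**Step 1: the built-in gap.** For three independent standard normals the expected minimum is -0.846, and the other two average +0.423, a gap of 1.27 SD. With correlation r and loading L, the expected gap between the own group and the other two is

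gap = 1.27 × L × √(1 − r).

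For L = 0.7: r = 0 gives 1.27 × 0.7 × 1 = 0.89 SD; r = 0.7 gives 1.27 × 0.7 × 0.548 = 0.49 SD; r = −0.4 gives 1.27 × 0.7 × 1.183 = 1.05 SD. The gap vanishes only if L = 0 or r = 1. A score correlated equally with all three composites is also not separated, but such a score does not help to classify anyone.

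**Step 2: eight equally weighted features per composite, none shared.** With correlation ρ between features, the composite variance is v = ρ + (1 − ρ)/8, so L = √v and r = ρ/v. For ρ = 0.3: v = 0.3 + 0.0875 = 0.3875, L = 0.62, r = 0.77. Rejection rates come from simulation (40,000 samples per cell, Monte Carlo half-width at most 0.5 points):

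| ρ | L | r | Single-feature gap (SD) | Single feature, 4 / 8 per group | Composite, 4 / 8 per group |
|---|---|---|---|---|---|
| 0 | 0.35 | 0 | 0.45 | 8% / 13% | 48% / 89% |
| 0.3 | 0.62 | 0.77 | 0.38 | 7% / 11% | 11% / 21% |
| 0.6 | 0.81 | 0.92 | 0.28 | 6% / 8% | 7% / 10% |

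The composite column matters if the composites are counted among the tested scores, which SAP 2.6 does not settle.

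**Step 3: a score that dominates its composite.** Table 2 uses the five factor-score variables in all three classes, often in opposing directions, and does not say that weights are equal. Loadings can then be higher, and composite correlations lower or negative, than in Step 2. ANOVA rejection rates:

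| Loading, n per group | r = −0.4 | −0.2 | 0 | 0.3 | 0.5 | 0.7 |
|---|---|---|---|---|---|---|
| 0.5, n = 4 | 15% | 13% | 12% | 10% | 8% | 7% |
| 0.7, n = 4 | 30% | 25% | 21% | 15% | 12% | 9% |
| 0.85, n = 4 | 49% | 40% | 32% | 22% | 16% | 11% |
| 0.7, n = 8 | 65% | 55% | 45% | 31% | 23% | 15% |

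At loading 0.7 and n = 4, the chance of at least one significant Tukey pair is nearly the same: 29/25/20/15/12/9%.

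**Step 4: scores outside the classifier.** A measure unrelated to the composites rejects in about 5%, as it should. A memory test correlating 0.3-0.5 with one composite rejects in 6-12% at 4 per group and 8-23% at 8 per group for r from 0.5 to 0 (up to 15% and 32% at r = −0.4).

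**The case against.** **The inflation may be small.** With 8 to 10 variables per class, any one score is a minor part of its composite, and Step 2 gives 6-8% at 4 per group. High loading and low composite correlation are also hard to combine when features are unshared. This stands: 30% and above is the high end, not the expected value. It does not rescue the test, because even a modest rejection rate answers a question that the assignment rule has already settled.

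**Characterization is the stated purpose.** Protocol 6.3.2 presents the screening as a description of deficits. A reader might infer that these ANOVAs are meant to confirm the subtypes; neither document says so. No stated hypothesis rests on them: Hypothesis A concerns matched versus mismatched treatment, and Objective 3.1 concerns imaging. This stands and limits the severity. But description needs means and SDs, and a p-value adds nothing to it.

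**The SAP sentence does not name the CVLT-II.** True. Its inclusion follows from Table 1 and the absence of any exception. If it was never intended, one sentence settles it.

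**The line between CVLT-II and the other memory tests is one of degree.** Step 4 concedes this. The difference is that classifier inputs are tied to the groups by definition, while an outside test can still carry information of its own. Hence those tests are kept, with a caveat.

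**Conclusion.** The point holds for scores and composites that feed the classifier. Their group differences are partly produced by the assignment rule, and ANOVA or Tukey p-values on them are not evidence for subtypes. At 4 per group under no true subtypes, the rate at a nominal 5% is about 6-8% for one of 8 equal, unshared features, 7-48% for a composite, and up to about 30% (loading 0.7) or 50% (loading 0.85) for a dominant score. It rises with N. Loadings, correlations and the Phase 2 sample size are assumptions; the circularity needs none of them.

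Three wider readings are not supported.
- **That all the group ANOVAs are circular.** Imaging measures unrelated to the composites keep their 5% level, and the matched-versus-mismatched analysis does not use these tests.
- **That the imaging ANOVAs should be relabelled exploratory.** Objective 3.1 declares primary measures for them, and how many imaging tests are run is a separate question.
- **That the classifier will be picked by its p-values.** Protocol 6.3.2.2 gives accuracy and stability as the criterion for considering other algorithms.

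This is a worthwhile correction to a secondary analysis in a 12-patient pilot, not a threat to its main comparison.

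**What to change.** Add to SAP 2.6:
1. Every score used by the final classifier, and other CVLT-II scores from the same trials, is reported by group descriptively, without ANOVA or Tukey p-values, with a note that the assignment rule partly produces the differences.
2. Neuropsychological group ANOVAs and Tukey tests are limited to measures that the classifier does not use.
3. Logical Memory, Visual Reproduction and the Rey figure may be tested under the Table 2 scheme, but are read as supportive only, because tests correlated with the composites keep some dependence on the grouping. If the final algorithm uses WMS variables, as one study cited in Protocol 6.3.2.2 did ("using hierarchical clustering of CVLT and WMS-R variables"), those scores become descriptive too.

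The cost is wording and table layout, with no new data. The downside is that CVLT-II group differences will have no p-values. Power for the tests that remain is unchanged.

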Aim 2. Aim 2 is to provide a preliminary test of the response to the three memory interventions. At baseline, TBI survivors will be evaluated for memory function in each of these three memory component processes using established neuropsychometric methods. Their experimental treatment allocation will be to the treatment targeting their most impaired memory component. In addition, each subject will serve as his/her own control, by engaging in a treatment targeted to another memory component ('mismatched' group).

Hypothesis A. The matched vs. mismatched group will show differential improvement in memory component function, with the former group benefitting to a significantly greater degree. (Primary measures: Memory component performance, encoding, consolidation, retrieval; secondary: cognitive function and quality of life).

Aim 3. Aim 3 is to establish links between the behavioral taxonomy of the three memory components and differences in brain structure and function documented with diffusion tensor imaging and functional connectivity analysis. This is a key first step in establishing brain-based metrics of neuroplastic change after memory therapy in our research program.

Objective 3.1. Identify specific and unique imaging signatures that distinguish patients with deficits in encoding, consolidation, and retrieval, respectively. Primary measures: structural measures of morphometry and white matter integrity (FA) and functional connectivity (cross correlation and total interdependence) in identified brain networks damaged in TBI.

Clinical Implications. This research has the potential to devise a method to match specific

subcomponents of memory impairment to specifically targeted memory interventions, thus maximizing recovery of memory and function. The results of this investigation will be used to refine the interventions, to evaluate cognitive and functional endpoints, and to power a larger clinical trial that will yield data enabling clinicians to match TBI patients to effective treatments based on their individual profile of memory dysfunction.

6. Research Plan:

6.1. Study Design. The proposed research will be conducted in three phases: Intervention Development, Patient Characterization and Classification, and Initial Testing of Treatment Efficacy.

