sentence (first list) or image (second list) that they created during encoding, and will then be asked to retrieve the target word again. Unsuccessful retrieval will be initially cued by the therapist. Prompted recall will also be recorded. This procedure will be repeated five times for each list, each followed by a retrieval phase. For each session, the dependent measure is the percentage of correct target words (out of 12) in spontaneous and cued recall for each list during the final exposure trial. For **FNP learning**, we will use a training approach adapted from Hampstead³⁹ and Stringer⁹. Training teaches patients to self-generate cues linking faces and names; patients will also be provided cues to standardize procedures and to encourage strategy development. For each FNP, participants will be directed to a salient facial feature (a visual cue like a long nose) and given a nickname that rhymes with the actual name (verbal cue) linking the feature to the name. Patients will be instructed to associate the visual and verbal cues by creating mental images that emphasize or exaggerate the relationship between cues. After initial learning, FNP's will be repeated five times. On each presentation, participants will be asked to recall the visual cue, then the verbal cue, and then finally the name. Dependent measure is the percent correct recall of visual cues, verbal cues, and names on the final trial of each list.

6.2.3. Errorless Learning (EL). EL refers to a group of techniques that promote recovery of memory abilities using procedures that explicitly prevent the patient from making errors during learning¹⁰. EL is based on the premise that errors during training become primed in long term memory via implicit memory mechanisms relatively spared in amnesia⁴⁰. Because of impairment in explicit memory consolidation that would normally provide corrective influence, these errors exert an unusually strong detrimental effect on relearning. While the standard interpretation of EL is that implicit memory is responsible for the treatment effect^{41,42}, it has been more recently shown that the EL advantage results from residual, though impaired, episodic memory consolidation due to temporal lobe damage^{43,44}. EL has been shown to be a promising tool in memory rehabilitation^{15,40,45}, at least for individuals without severe executive deficits⁴⁶.

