6.2.3.1. Procedure. Six biweekly sessions of EL will be conducted, each using two VPA lists and two FNP lists. During EL, the word pairs (e.g., "candle-table") or face-name pairs will be presented in horizontal arrangement on a computer screen at a rate of 1 per 6 seconds with no encoding instructions. After initial presentation, the cue will be presented without the target. For VPA learning, the cue word in each pair ("candle - _____") will be presented, and the participant will be asked to provide the second (target) word, ***but only if they are certain they can retrieve it accurately. Guessing is explicitly discouraged.*** If the participant cannot provide the word within 3 seconds, the word appears on the screen for 3 seconds and the participant is asked to read the pair aloud. During training, each list will be presented five times in this fashion. The dependent measure is the percent correct target words produced (out of 12) during the fifth exposure trial for each list. The procedure will be repeated for the second VPA list and then for the two FNP lists, yielding 4 accuracy measures (percent correct) for each session.

6.2.4. Retrieval Practice (RP). Some authors have argued that practicing retrieval during learning is an essential feature of successful learning^{10,47}. Effects of RP are most robust when retrieval is effortful, successful and spaced over time^{48,49}. If retrieval of a learned item is practiced shortly after it is learned, but before it is forgotten, subsequent recall is enhanced, a phenomenon known as the "testing effect"⁴⁷. RP has been used recently to improve performance of memory-impaired patients with multiple sclerosis⁵⁰ and M-STBI^{11,19}.

6.2.4.1. Procedure. Six biweekly sessions of RP will be conducted. We will follow procedures outlined in Sumkowski et al¹⁹, who demonstrated efficacy of RP in a small group of patients with M-STBI and chronic memory deficits. For each session, two sets of 12 VPA's and 12 FNP's will be used. Paired stimuli will be presented together for 6s on a computer screen, and the participant will be asked to read the VPA or say the name (FNP) aloud. Following this, 3 6s filler pairs (other VPA's or FNP's) will be presented. Then, a 5s cued

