recall test (candle-_____), followed by a 1-s feedback screen (candle-table) will be presented, followed by another six 6s filler trials and another 5s cued recall test and 1s feedback. This continues until all 12 VPA's or FNP's are given. After VPA is complete, FNP is administered (counterbalanced). After a brief delay, the participant completes two separate delayed cued recall tests (VPA, FNP, counterbalanced). The procedure is repeated for the second set of VPA's and FNP's. Dependent measure: Percent correct scores on the delayed recall test for each of the two VPA and two FNP sets, recorded each session.

6.2.5 Manualization and Fidelity Testing. During Phase 1, session-by-session procedures, including instructions to therapists and patients, stimuli and stimulus presentation schedules, methods of data collection, and permissible procedural variations will be formalized into a treatment manual for each of the three interventions. Six Master's level therapists will be trained in all three interventions, and will practice administering them to volunteer participants. At the end of Phase 1, each therapist will administer each treatment to a Veteran participant with M-STBI. Each session will be video recorded for evaluation of treatment fidelity by the study team^{51,52}, which will review session recordings and will rate the degree to which the therapist adhered to the following aspects of the protocol: communication of content to the participant (consent, rationale for treatment, instructions for engaging in training), accurate use of cues, selection of stimulus materials, recording of data, and adherence to designated treatment schedules. We will develop a rating sheet that provides feedback to therapists on their adherence to the manualized protocol⁵³.

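### SAP 2.6 compares matched with unmatched treatment only within each person, where match cannot be told from treatment or order, and states no pooled estimate for Hypothesis A

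*SAP*

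**What the plan says.** Hypothesis A (Protocol 5, Aim 2) compares matched with mismatched treatment, "with the former group benefitting to a significantly greater degree". The Clinical Implications paragraph lists among the uses of the results "to power a larger clinical trial that will yield data enabling clinicians to match TBI patients to effective treatments".

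Protocol 6.4.2 and Table 4 place one participant in each of 12 treatment orders, four per deficit group. Each person receives one matched and one mismatched treatment, in six-session blocks. The section expects carryover to be small, relies on counterbalancing, and notes that first and second position can be compared.

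SAP 2.6 then states: "Data from Phase 3 will be analyzed by comparing effect sizes of matched and unmatched treatments at the individual subject level". The tools are non-overlap, improvement rate and level, and Tau-U; interrupted time-series or regression methods and a last-day comparison are to be explored. The across-person analyses of response are exploratory predictors based on the composite scores and a "hierarchical linear regression in which severity is coded as average z-score on memory indices derived from phase 2, and patient grouping is dummy-coded". Neither states a match term. Outcomes are the session scores "as well as post-treatment and 1-month follow-up probes".

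The session scores differ by treatment:
- Memory strategy training, MST (6.2.2.1), word pairs: "percentage of correct target words (out of 12) in spontaneous and cued recall for each list during the final exposure trial".
- Errorless learning, EL (6.2.3.1): "The dependent measure is the percent correct target words produced (out of 12) during the fifth exposure trial for each list".
- Retrieval practice, RP (6.2.4.1): "Percent correct scores on the delayed recall test for each of the two VPA and two FNP sets".

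**The concern.** Counterbalancing works only across people. In one participant, the matched-minus-mismatched difference is also treatment X minus treatment Y and one block minus the other. An individual effect size therefore cannot say which of the three produced it. A treatment gap is plausible from the measures alone, since RP is scored on a delayed test and the other two on the last training trial. Post-treatment and 1-month probes, even if identical across treatments, would leave the aliasing with treatment and order in place.

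Two things are at stake. A treatment, measure or order gap can be read as evidence for matching in individual patients. And the stated hypothesis receives no group-level estimate or interval, although a match estimate with its uncertainty is a direct input for planning the larger trial.

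**Working it through.** **Inputs.** The orders are those of Table 4 (1 = MST, 2 = EL, 3 = RP). The documents give no alpha, power, effect size, SD, dropout rate or treatment or period gap for Phase 3. All such values below are assumptions: two-sided alpha 0.05, a match effect of 10 percentage points, and an SD of the within-person difference of 10, 15 or 20 points.

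**Plan's own figure.** 3 groups × 4 orders = 12 participants, as stated.

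**Model for one person.** Let M be the match effect, t1, t2 and t3 the treatment levels, and p the second-minus-first gap. The matched-minus-mismatched difference D is:

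| Group | Orders, matched first | D | Orders, matched second | D |
|---|---|---|---|---|
| Encoding | 12, 13 | M + t1 − t2 − p; M + t1 − t3 − p | 21, 31 | M + t1 − t2 + p; M + t1 − t3 + p |
| Consolidation | 21, 23 | M + t2 − t1 − p; M + t2 − t3 − p | 12, 32 | M + t2 − t1 + p; M + t2 − t3 + p |
| Retrieval | 31, 32 | M + t3 − t1 − p; M + t3 − t2 − p | 13, 23 | M + t3 − t1 + p; M + t3 − t2 + p |

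**Individual level, M = 0.** If one treatment scores g higher, D = +g in the 4 people for whom it is matched, −g in the 4 who receive it as mismatched, and 0 in the other 4. So 8 of 12 are false. A gap p alone gives a false effect in all 12 (6 for, 6 against). Together, assumed g = 5 and p = 5 give values from −10 to +10; g = 15 and p = 10 give −25 to +25.

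**Deficit-group level.** Order cancels (two matched first, two second), but the mean is M + (own treatment − average of the other two). With M = 0 it is +g in the favoured treatment's own group and −g/2 in each other group. Match plus treatment has rank 2, and treatment alone also has rank 2, so match is aliased.

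**All 12.** Each treatment enters 4 times with plus and 4 times with minus, and p enters 6 times each way. The mean of D is therefore M. The match column has zero cross-products with the treatment and period columns, so the variance is SD²/12 with or without adjustment. Residual df = 12 − 4 = 8 (match, two treatment contrasts, period), against 11 unadjusted.

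**Precision, 12 completers.**
- 95% half-width: 2.306/√12 = 0.67 SD, against 2.201/√12 = 0.64 SD unadjusted. At SD 10/15/20 the adjusted half-width is 6.7/10.0/13.3 points.
- Effect detectable with 80% power (noncentral t): 0.92 SD, against 0.89 SD.
- Power for 10 points: 86/53/33% with 8 df, against 88/56/35% with 11 df and no gaps.

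**Dropout (every subset of lost participants).** With one lost: variance factor 0.0938, 7 df, half-width 0.72 SD, power 80/47/29%. With three lost: 0.113 to 0.160, 5 df, 0.86 to 1.03 SD, power 52–67/27–36/18–23%.

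**Why adjust rather than average the 12 differences.** With gaps, an unadjusted average puts them into its error term. At SD 10, simulated power falls from 88% to about 78% (g = 5, p = 5) or 26% (g = 15, p = 10). With 1 to 3 participants lost, its bias reaches 0.9 to 2.8 points, or 2.3 to 6.7 points. The adjusted model stays unbiased if effects are additive.

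**Biases that remain.**
- A boost c to the second block only after matched-first training lowers D in 6 of 12: −6c/12 = −c/2. For assumed c of 5 to 10, −2.5 to −5.
- The consolidation group, described in 6.3.2.2 as forgetting rapidly, loses m extra on the delayed RP score (orders 23 and 32): +2m/12 = +m/6. For assumed m of 6 to 18, +1 to +3.
- The retrieval group, for which RP is matched, loses m there: −4m/12 = −m/3, or −2 to −6.

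**The case against.** Individual analysis is a declared choice. Protocol 6.4.2 picks a design meant for comparing two treatments in one person, Aim 2 is called preliminary, and 6.3.2 calls the study a pilot. SAP 2.6 is not silent on time or testing: Tau-U tests two treatments after trend adjustment, and interrupted time-series methods will be explored. The pooled estimate is itself fragile. Match is a contrast within the group-by-treatment interaction, so a deficit group's particular difficulty with one measure leaks into it, and power is only 33 to 53% at SDs of 15 to 20. The figures for an unadjusted average concern an analysis the SAP does not propose. Part of the SAP, including the Section 2.2 it cites for the outcome variables, is not in the reviewed text.

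Much of this stands as a limit. The study is a pilot, per-person tests exist, trend is partly handled, and the figures for the unadjusted average show only why the added model should adjust. But Tau-U and time-series methods act within a person: they cannot separate match from treatment, nor remove a step at the single switch. Keeping the individual analyses does not conflict with adding a pooled one. Low precision is a reason to report an interval, not to leave the estimate out.

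**Conclusion.** The concern holds and should be fixed. As written, SAP 2.6 can turn a treatment, measure or order gap into an apparent match effect in 8 to 12 of 12 participants, and averaging within a deficit group does not remove a treatment gap. Those counts follow from Table 4 alone, taking each gap separately. The same table makes the pooled match effect estimable with 8 df, but SAP 2.6 does not use this.

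The pooled estimate rests on additive effects on the percent scale and on carryover that does not depend on match. It is an average over the three deficit groups, not a group-specific effect. Power and half-widths in points rest on the assumed SDs and match effect. The session measures are taken from Protocol 6.2, because SAP Section 2.2 was not available.

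**What to change.** Keep the individual effect sizes. In SAP 2.6, add as the group-level analysis of Hypothesis A a model over all 12 participants with a participant effect, fixed effects for match, treatment and period, and small-sample degrees of freedom. Report the match effect with a 95% CI. Fit it to the block level and to the within-block slope or improvement, since the hypothetical example in 6.4.2 refers to both. Name one leading outcome in advance, including whether it comes from the verbal pairs or the face-name pairs.

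As a check on the measurement difference, repeat the model on change over each block in the Table 5 memory measures, which Protocol 6.5 collects before treatment and after each treatment with the same tests.

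State the limits beside the result: additivity, match-dependent carryover, and group-specific difficulty with one treatment's measure. Present it as an estimate with an interval, not as a well-powered test.

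The cost is SAP wording and one model on data already planned: 3 degrees of freedom, and with 12 completers an increase in half-width of about 0.03 SD. No visits, tests or participants are added.
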